5.4 Compliance with Study Procedures

Patients will receive the study treatment as outlined in Section 6.0. The details of the study treatment will be documented in the eCRF and IMP accountability forms as applicable.

All study treatment related procedures will be performed in the hospital or clinic by qualified health care personnel. All instances of noncompliance and all resulting protocol deviations will be recorded in the eCRF.

6.0 TREATMENT OF PATIENTS

6.1 Drug Supply and Handling Procedures

6.1.1 Investigational Medicinal Product, APR-246

The IMP will be manufactured according to Good Manufacturing Practice (GMP), and labeled according to GCP, GMP and the national requirements for each site. The labels will comply with the legal requirements of the country. They will include storage conditions for the drug but no information about the study.

The IMP will be distributed in vials to the pharmacies of each participating study center. The APR-246 substance will be diluted in 0.9% sodium chloride solution at the appropriate concentration for infusion for each patient.

At the pharmacies, the IMP vials are to be stored at 2-8°C. At the pharmacies and at the study centers, the prepared APR-246 study product (diluted in sodium chloride solution) is to be stored at not more than 25°C. The infusion should be completed within 24h from the time of preparation (see Study Manual).

Detailed instructions on vial concentration, preparation and dispensing can be found in the Pharmacy File.

6.1.2 Carboplatin

Carboplatin will be provided from the pharmacy stock. The carboplatin bag used for administration will be labeled according to the local routines and regulatory requirements. The hospital will be responsible for ordering carboplatin. The manufacturer and batch numbers will be documented.

Please refer to the Summary of Product Characteristics for further information on carboplatin.

6.1.3 Pegylated Liposomal Doxorubicin (PLD) Hydrochloride

PLD will be provided from the pharmacy stock. The PLD bag used for administration will be labeled according to the local routines and regulatory requirements. The hospital will be responsible for ordering PLD. The manufacturer and batch numbers will be documented.

Please refer to the Summary of Product Characteristics for further information on PLD.

6.2 IMP Accountability/Disposition of Clinical Trial Supplies

IMP accountability records will be maintained for all clinical trial supplies.

IMP accountability records will be kept at the pharmacy and at the study centers. The pharmacy must maintain accurate records demonstrating date and amount of IMP received, to whom and by whom administered, and accounts of any IMP accidentally or deliberately destroyed.

The Investigator is responsible for keeping records to ensure that:

- a. Deliveries of IMPs are correctly received and recorded by a designated person.
- b. Study medications are handled and stored safely and properly.
- c. Study medications are dispensed only to study patients in accordance with the protocol.
- d. All unused medication and empty containers are stored until they have been checked by the study monitor.
- e. It is possible to reconcile records of all used and unused stocks as confirmed by the Investigator's signature.

The IMP is the property of Aprea Therapeutics AB and must not be passed on to third parties. Any discrepancies between returned and expected returned IMP should be explained.

6.3 Method of Assigning Patients to Treatment Groups

Up to 400 patients will be centrally registered and randomly assigned study treatment in a 1:1 ratio to receive either:

- Arm A: APR-246 treatment on Days 1 to 4, with carboplatin and PLD administered concurrently on Day 4 (treatment repeated every 28 days for up to six cycles) or
- Arm B: Carboplatin and PLD alone administered on Day 1 of each 28-day cycle, repeated for up to six cycles.

Patients will be stratified at randomization by:

- Platinum-free Interval after previous platinum based regimen. 6-12 months vs. 12-24 months
- Prior Lines of Platinum Treatment. One line vs. Two lines
- BRCA status. known positive vs. other

The schema for the study is shown in Figure 2 below.

[figure not shown]

Figure 2. Phase II Schema

6.4 Treatment Administration

6.4.1 Treatment Arm A: APR-246 with carboplatin and PLD

Patients will receive a fixed dose of 4.5 g APR-246 (1.5 g of the dose during first 45 minutes followed by 3 g of the dose during 5 hours 15 minutes) on Days 1 to 4 with carboplatin AUC 5 and PLD 30 mg/m² on Day 4 (Figure 3). Carboplatin and PLD administration to be given on Day 4 only should commence 2 hours after the start of the APR-246 infusion. Further administration of APR-246 (repeated in 28-day cycles) will commence three days prior to subsequent chemotherapy cycles, with the fourth dose administered the same day as the chemotherapy.

[figure not shown]

Figure 3. Treatment Administration for Patients Receiving APR-246

Note: The entire dose should be given even if the infusion needs to be extended beyond a total time of 6 hours (e.g. due to slightly larger start volume in prefilled infusion bags).

APR-246 Treatment Duration

Treatment will be repeated every 28 days for up to 6 cycles in the absence of disease progression or unacceptable toxicity. Supportive therapy, including growth factors, can be given as per institutional standard of care.

Carboplatin Dosing

The dose of carboplatin will be calculated as per standard practice at that hospital. Patients will start at carboplatin with an AUC 5.

Pegylated Liposomal Doxorubicin Dosing

The dose of PLD will be calculated based on the body surface of the patients at 30 mg/m^2 as per standard practice at that hospital.

6.4.2 Treatment Arm B: Carboplatin and PLD alone

Patients will receive carboplatin AUC 5 plus PLD at 30 mg/m^2 on Day 1 of each cycle. Treatment will be repeated every 28 days for a total of up to six cycles in the absence of disease progression or unacceptable toxicity. Supportive therapy will be given as per institutional standard of care. Patients randomized to Arm B will not receive APR-246.

Carboplatin Dosing

The dose of carboplatin will be calculated as per standard practice at that hospital. Patients will start at carboplatin with an AUC 5.

Pegylated Liposomal Doxorubicin Hydrochloride Dosing

The dose of PLD will be calculated based on the body surface of the patients at 30 mg/m^2 as per standard practice at that hospital.

6.4.3 Treatment of Adverse Events of the Central Nervous System related to APR-246

If a patient reports any clinical adverse event of any grade during the administration period of APR-246 that could be considered to originate from the central nervous system (e.g. dizziness, vertigo, nausea) then the patient will be given a rescue medication as per the institutional standard of care (Table 1).

Table 1. Rescue Medications for use with APR-246

Indication	Supportive Measure
Central Nervous System symptoms (Treatment and Prevention)	Prochlorperazine 10 mg orally tid ^a or other as per the institutional standard of care Start Day -1 prior to APR-246 administration
Persistent CNS symptoms	Cyclizine 50 mg IM or other as per the institutional standard of care

a. Prochlorperazine 10 mg orally tid (three times daily). To continue until end of Day 4 of the cycle. When used prophylactically for future treatment, start the day prior to the Day 1 administration of APR-246 of each cycle (as needed).

If during the infusion the patient continues to remain symptomatic intramuscular administration of cyclizine 50 mg may be considered.

6.5 Dose Modifications

6.5.1 Modifications for APR-246 due to Adverse Events during Infusion

If a patient in Arm A has any clinical adverse event \geq grade 3 during the APR-246 infusion, the infusion should immediately be stopped. The type, severity and duration of the adverse event should be carefully assessed as well as the relationship to APR-246.

If the adverse event is considered to be unrelated to APR-246, the infusion may be resumed within 2 hours.

If the adverse event is considered to be related to APR-246, as long as all symptoms resolve to CTCAE Grade 1 or less within 2 hours, the infusion may be resumed.

In case of re-challenge, the infusion should resume at the same infusion rate (the same dose per time unit) as the initial infusion. If no symptoms occur during re-challenge, the infusion can continue until the whole dose is given and the treatment can continue according to the protocol.

If the same symptoms do occur or increase in severity during re-challenge the infusion should be stopped.

If the event lasts longer than 2 hours, then the remainder of the APR-246 infusion for that day should be discarded. If the patient has recovered sufficiently by the next day, the remainder of the planned course should be administered.

After an adverse event considered as related, a single level dose reduction of APR-246 is allowed (Table 2). The rationale for the suggested dose reductions is the steep relation between C_{max} and dose, revealed by modeling based on an extended population PK analysis (Section 2.7.1.1). If more than two dose reductions of APR-246 are required, APR-246 must be discontinued.

The type, severity and duration of the symptoms, adverse event and infusion timings (start and stop) should be carefully documented in the patient's medical charts as per trial procedures.

Table 2. Dose Modifications of APR-246

Dose Modification	APR-246 Dose
Current Dose Level (DL)	APR-246 4.5 g 1.5 g (for first 45 minutes) + 3 g (for 5 hours 15 minutes)
First dose reduction DL-1	APR-246 4.0 g 1.33 g (for first 45 minutes) + 2.67 g (for 5 hours 15 minutes)
Second dose DL-2	APR-246 3.5 g 1.16 g (for first 45 minutes) + 2.34 g (for 5 hours 15 minutes)

The rationale behind this dose reduction scheme is the steep relation between C_{max} and dose, e.g. the suggested 11% and 22% reductions in dose result in 19% and 33% lowering of the average C_{max} , respectively (Section 2.7.1.1).

6.5.1.1 APR-246 Infusion and Systemic Chemotherapy Delays

The days 1 to 4 APR-246 administration, together with the day 4 chemotherapy, are to be regarded as one treatment cycle and must be administered consecutively.

On day 1, prior to APR-246 administration, the hematological status of the patient should be assessed. If the patient has any hematological adverse event that would prevent systemic chemotherapy administration on day 4, the APR-246 infusion and systemic chemotherapy should be delayed until recovery (see Section 6.5.2.1).

If a patient has any adverse event on days 2, 3 or 4 prior to the APR-246 infusion which, in the opinion of the Investigator, would prevent systemic chemotherapy administration, the remainder of the planned APR-246 administration should be stopped. Once the patient has recovered sufficiently to receive chemotherapy, the whole treatment cycle (consisting of days 1-4 APR-246 and day 4 chemotherapy) should be restarted as previously planned.

If APR-246 and/or systemic chemotherapy are delayed, the reasons for delay should be recorded in eCRF.

6.5.2 Dose Modifications for Systemic Chemotherapy

For typical hematological (Table 3 and Table 4) and non-hematological (Section 6.5.2.2) adverse events seen with carboplatin and PLD, the dose modifications specified below should be applied. However, if any adverse events occur that are not typical or that are considered unusual, the Sponsor should be consulted prior to re-treating the patient.

If due to adverse events the patient is unable to continue treatment with PLD, the Investigator may consider continuing with carboplatin monotherapy and APR-246 in Arm A to a total of six cycles (including all prior combination chemotherapy cycles).

If due to adverse events the patient is unable to continue chemotherapy with both PLD and carboplatin, the patient may continue monotherapy APR-246 up to 6 courses in total if the following criteria are met:

- There is CA-125 reduction suggestive of treatment benefit (eligible patients)
- Latest radiological scans shows evidence of response
- Patient is evaluated as not having symptoms suggestive of progressive disease
- The Investigator assessment is that APR-246 monotherapy is of continued benefit to the patient
- APR-246 administration has been approved by the Sponsor.

6.5.2.1 Hematological Toxicity and Dose Modifications

The absolute neutrophil count (ANC) must be $\geq 1.50 \times 10^9/L$ and the platelet count must be $\geq 100 \times 10^9/L$ in order to administer full doses of carboplatin and PLD in each cycle as assessed on day 1. In the event of an $ANC < 1.0 \times 10^9/L$, hematological assessment should be performed twice a week until recovery of ANC to $> 1.0 \times 10^9/L$. Patients should be monitored prior to each dose for platelet and neutrophil counts, and at the discretion of the Investigator, if necessary, the dose of carboplatin and/or PLD may be either reduced or withheld in the presence of hematological toxicity according to the following scale (Table 3):

Table 3. Dose Modification of Systemic Chemotherapy for Hematological Toxicities

Hematological Assessment on Day 1 of a Cycle:			
ANC ($\times 10^9/L$)		Platelet Count ($\times 10^9/L$)	Dose Modification
≥ 1.5	and	≥ 100	Administer full dose of Carboplatin and PLD
< 1.5	and/or	< 100	Delay cycle for 7 days. If within normal acceptable parameters (as above) proceed with dose reductions of carboplatin to AUC 4 and PLD 25 mg/m ² .
Dose reduction to carboplatin AUC 4 and PLD 25 mg/m ² is also required in the following circumstances:			

• $ANC < 0.5 \times 10^9/L$ for > 7 days• An episode of febrile neutropenia (temp $\geq 38.5^\circ C$ and $ANC < 1.0 \times 10^9/L$)• Platelets $< 25 \times 10^9/L$, or bleeding requiring a platelet transfusion			

Growth factors:

- For patients who have a prolonged neutropenia, Investigators may administer growth factors to aid white cell count recovery. This should be given per the package insert.
- Patients who the Investigator considers to be at risk for developing neutropenia (considering bone marrow tolerance with prior chemotherapy or neutropenia while on the PiSARRO study)

that could affect their ability to receive study treatment per the study protocol, should consider administering prophylactic growth factor per the package insert.

For patients in Arm A:

- If hematological recovery is inadequate by Day 42 of any cycle, the Investigator should discuss appropriate patient management with the Sponsor before allowing the patient to continue with study drug treatment. If the patient is showing signs of response, the Investigator may retain the patient in the study, but should assess the potential for further prolonged periods of marrow suppression and the associated adverse events as part of this decision process.
- In the event that a patient requires a second dose reduction of systemic chemotherapy or the initial recovery of hematologic parameters took longer than 14 days even with growth factor support, the Investigator may also consider a single level reduction in the dose of APR-246 in conjunction with a further dose reduction of chemotherapy per Table 4.

Table 4. Dose Modification of Systemic Chemotherapy for Hematological Toxicities in Arm A

Chemotherapy Modification	Treatment Delay	APR-246 Dose Modification
Initial Dose Reduction	Less than 14 days	None
	14 days or more	Reduce one level
Second Dose Reduction	Any	Reduce one level

For patients in Arm B:

- If hematological recovery is inadequate by Day 42 of any cycle after cycle 2, the Investigator should discuss appropriate patient management with the Sponsor.

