7.0 STUDY PROCEDURES

7.1 Schedule of Study Procedures

Study evaluations are summarized in the Table 9 and Table 10 below and described in Sections 7.2 through 7.2.7.

The Principal Investigator is responsible for ensuring that all staff involved in the study are familiar with the content of this section.

Table 9. Schedule of Study Evaluations in Arm A

	Pre-treatment 1	Cycle 1					Cycle 2 and subsequent cycles					EoT ¹⁴	FU ¹⁵
		1	2	3	4	5	1	2	3	4	5	25- 28	
Day													
Eligibility Criteria	X												
Registration/Randomization and Informed Consent	X												
Medical History	X	X*											
Quality of Life Questionnaires	X											X ¹⁰	X
Tumor Assessment ²	X											X	X
Physical Exam/ECOG	X	X*					X					X	X ¹¹
Vital Signs	X	X	X	X	X		X	X	X	X			
Hematology/Coagulation	X	X*					X*						X
Blood Chemistry	X	X*					X*						X
Creatinine Clearance	X												
CA-125		X*					X*					X	X ⁸
Urinalysis	X	X*					X*						
Serum Pregnancy Test (women of child bearing potential)	X												
LVEF ³	X						X ³						
ECG ⁴	X												X
Tumor Biopsy ⁵ (optional)	X			X									
Exploratory Biomarkers	X	X		X	X ¹³	X ⁷		X ⁷	X ^{7,13}			X	X ⁸
Administer APR-246		X	X	X	X		X	X	X	X			
Administer Chemotherapy				X					X				
Adverse Events and Concomitant Medication	X	X	X	X	X	X	X	X	X	X	X		
Survival				X									X ¹²
Pharmacokinetics ⁶		X	X	X									

Examinations marked * need not be repeated if already performed within 3 days prior to Day 1.

1. Pre-treatment evaluations are to be performed within 28 days of Day 1 of Cycle 1.
2. A CT scan/MRI should be performed at pre-treatment (within 4 weeks prior to day 1 of study treatment) and at the end of cycle 2 (within 7 days prior to the start of cycle 3), and at the end of cycle 4 (within 7 days prior to the start of cycle 5), after the last cycle, 2 months (\pm 2 weeks) after the end of treatment (EoT) visit and every 3 months (\pm 2 weeks) thereafter, until the documented disease progression, as determined by the Investigator at each site and defined by RECIST v1.1. Confirmatory scans to be done at least 28 days after scan performed post last treatment cycle for all patients initially assessed as having a radiological response.

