- **Pharmacokinetics:** Arm A only. On Cycle 1, days 1, 2, and 4; please refer to Section 8.4 for PK sampling time points.
- **Exploratory biomarkers:** Arm A blood samples. Cycle 1 on days 1, 4 and 5. Cycle 2 on days 1, 4 and 5. Cycle 6 on day 1. Arm B blood samples. Cycle 1 and 2 on days 1 and 2. Cycle 6 on day 1. Refer to laboratory manual for detailed instructions.
- **APR-246 administration:** Arm A only on days 1, 2, 3 and 4.
- **Chemotherapy administration (Carboplatin and PLD):** Arm A on day 4. Arm B on day 1.
- **Adverse Events:** All adverse events since the last visit should be recorded. Even though pre-medicated, patients should be closely monitored.
- **Concomitant medications.**

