7.3.3.6 Adverse Events based on Examinations and Tests

The results from protocol mandated laboratory tests, vital signs, ECGs and other safety assessments will be summarized in the Clinical Study Report. Deterioration as compared to pre-treatment in these parameters will therefore only be reported as AEs if they fulfill any of the criteria for a SAE or are the reason for modifying the study treatment unless clearly due to progression of disease under study (see Section 7.3.3.8).

If deterioration in a laboratory value, vital sign, ECG, or other safety assessment is associated with clinical events, the clinical event will be reported as an AE and the associated laboratory result or other finding will be considered as additional information. Wherever possible the reporting Investigator will use the clinical, rather than the laboratory term (e.g., anemia versus low hemoglobin value). In the absence of clinical events, clinically relevant deteriorations in non-mandated parameters should be reported as AE(s).

Deterioration of a laboratory value that is unequivocally due to disease progression should not be reported as an AE.

Any new or aggravated clinically relevant abnormal medical finding at a physical examination as compared with the pre-treatment assessment will be reported as an AE.

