9.5.1 Safety Analysis

Safety data will be summarized for the safety evaluable population. These data will include adverse events and laboratory parameters. Adverse event terms will be coded using the Medical Dictionary for Drug Regulatory Activities (MedDRA®, version 16.0 or higher). Adverse events will be summarized by body system, preferred term, severity, and relationship to treatment. Serious adverse events, deaths, and AEs leading to early discontinuation of study drug will be summarized. Laboratory parameters will be summarized by maximum NCI-CTCAE-4.0 severity grade and also by change from pre-treatment to scheduled time points using descriptive statistics. Laboratory parameter listings will include the normal ranges for each parameter. Each value will be classified as falling above, below, or within the normal range.

Data summaries will include only treatment-emergent adverse events (TEAEs), defined as events occurring on or after Day 1 Cycle 1 up to and including 30 days after last dose.

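### From cycle 2 the scheduled Day 1 blood count falls 25 days after chemotherapy in Arm A but 28 days after it in Arm B, and the laboratory comparison in Section 9.5.1 does not allow for the difference

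*Combined protocol and SAP*

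**What the plan says.** Section 6.3 defines Arm A as "APR-246 treatment on Days 1 to 4, with carboplatin and PLD administered concurrently on Day 4" and Arm B as carboplatin/PLD on Day 1. Both run in 28-day cycles. Section 7.2.4 repeats the chemotherapy days: "Arm A on day 4. Arm B on day 1".

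The count that decides dosing is on Day 1 in both arms. Section 6.5.2.1 requires ANC of at least 1.5 and platelets of at least 100 (both × 10⁹/L) "in order to administer full doses of carboplatin and PLD in each cycle as assessed on day 1", and Table 3 is headed for Day 1 with no distinction by arm. For Arm A, Section 6.5.1.1 adds: "On day 1, prior to APR-246 administration, the hematological status of the patient should be assessed". Under Table 3 a low count leads to a 7-day delay and then reduced carboplatin and PLD.

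Day 1 is also the only routine on-treatment hematology in Section 7.2.4; repeats are only to follow up adverse events. Table 9 allows a look-back, "Examinations marked * need not be repeated if already performed within 3 days prior to Day 1", and Table 10 has the same note.

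Section 9.5.1 summarizes laboratory parameters by maximum CTCAE grade and "by change from pre-treatment to scheduled time points using descriptive statistics". Under Section 7.3.3.6, a deterioration in a protocol-mandated laboratory test becomes an adverse event only if it meets a seriousness criterion or if such changes "are the reason for modifying the study treatment".

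**The concern.** The two arms share a calendar label, Day 1, but not the time since the last myelosuppressive dose. If counts are still climbing between 25 and 28 days after carboplatin/PLD, a patient who crosses a limit in that gap fails the Arm A check and would have passed the Arm B check. The reverse cannot happen.

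A secondary objective is the safety of the combination compared with carboplatin/PLD alone. A summary of change at scheduled time points would show lower ANC, platelets and perhaps hemoglobin in Arm A even if APR-246 did nothing to the marrow. Any extra Day 1 failure that leads to a treatment change can also enter the adverse event tables through Section 7.3.3.6. A reader of the safety report could take both as marrow toxicity of the drug. Nothing in the documents mentions the offset or adjusts for it.

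**Working it through.** **Step 1: the day count (exact).**

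Inputs: cycle length 28 days; chemotherapy day 4 (Arm A) and 1 (Arm B), from Sections 6.3 and 7.2.4.

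Days from chemotherapy to the next Day 1 = (28 + 1) − chemotherapy day.
- Arm A: 29 − 4 = 25.
- Arm B: 29 − 1 = 28.

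Cross-check: Section 6.4.1 says APR-246 starts three days before the next chemotherapy, so Arm A is 28 − 3 = 25. The two routes agree. Chemotherapy to chemotherapy is 28 days in both arms.

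The 3-day offset recurs at every time point tied to the cycle calendar:

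| Time point | Arm A, days since chemotherapy | Arm B |
|---|---|---|
| Day 1 of next cycle | 25 | 28 |
| With 3-day look-back | 22-25 | 25-28 |
| Recheck after 7-day delay | 32 | 35 |
| Day 42 of the cycle | 38 | 41 |
| End-of-treatment visit, days 28-35 of cycle 6 | 24-31 | 27-34 |

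**Step 2: direction.** With the same recovery path and the same limit, an earlier test can only find more patients below the limit while counts are rising, and the same number if they are flat.

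**Step 3: size (illustration only).** The documents give no recovery curve, failure rate or between-patient spread. Assume no APR-246 effect on the marrow, lognormal counts with log-SD s of 0.35 or 0.5, log recovery r per day between days 25 and 28, and an Arm B failure rate p_B. The Arm A failure rate is then

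p_A = Φ(Φ⁻¹(p_B) + 3r/s).

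Example: p_B = 0.10, r = 0.04, s = 0.5 gives Φ(−1.282 + 0.240) = Φ(−1.042) = 0.149. With s = 0.35 it gives Φ(−1.282 + 0.343) = 0.174.

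| r per day | p_A if p_B = 5% | p_A if p_B = 10% | p_A if p_B = 20% |
|---|---|---|---|
| 0 (plateau) | 5% | 10% | 20% |
| 1% | 5.6-5.9% | 11.1-11.6% | 21.7-22.5% |
| 2% | 6.4-7.0% | 12.3-13.3% | 23.5-25.1% |
| 4% | 8.0-9.6% | 14.9-17.4% | 27.4-30.9% |
| 8% | 12.2-16.9% | 21.1-27.6% | 35.9-43.8% |

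The share of Arm A failures due to timing is (p_A − p_B)/p_A. It is zero at a plateau, about 8-10% at 1% per day with s = 0.5 (p_B = 20% and 10%), and about 70% at the extreme (r = 8%, s = 0.35, p_B = 5%).

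**Step 4: a differently built model.** Let time to recovery be normal with SD σ and the same in both arms. Then μ = 28 − σΦ⁻¹(1 − p_B) and p_A = 1 − Φ((25 − μ)/σ). For p_B = 10% and σ = 5: μ = 28 − 5 × 1.282 = 21.6 and p_A = 1 − Φ(0.68) = 25%. Over σ = 3 to 10 days, p_A runs from 39% down to 16%. The direction agrees, but the size depends on the model.

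**The case against.** **The effect is conditional.** It needs patients who cross a limit between days 25 and 28. If counts have plateaued by day 25 there is none, and every size above rests on assumed inputs. This stands. A reader might infer that a fixed, large fraction of Arm A's low counts is artefact; the documents do not support any particular figure.

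**It is part of the regimen.** Starting APR-246 three days before chemotherapy is how Arm A is given, and the safety objective compares regimens. Delays and reductions triggered on Day 1 really happen to Arm A patients. This stands too. A reader might infer that PFS is no longer a fair comparison because the chemotherapy backbone could be reduced more often in Arm A. Section 9.4 analyzes all randomized patients as randomized, so the PFS test remains valid for the regimens as assigned. What is affected is attribution to marrow toxicity of APR-246.

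**The plan does not tabulate delays or reductions.** Section 9.5.1 lists adverse events, serious events, deaths, discontinuations and laboratory parameters. It is therefore wrong to say that a planned summary of delays is biased; there is none.

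**Dosing is not mechanical.** Section 6.5.2.1 leaves reduction or withholding to the investigator's discretion and allows growth factors. Its other reduction triggers (prolonged ANC below 0.5, febrile neutropenia, platelets below 25 or bleeding requiring transfusion) are not tied to the Day 1 count. These features may dilute the effect. Section 7.3.3.6 also applies to both arms, so only the extra timing-driven events would fall on Arm A.

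**The look-back gives overlap.** An Arm B count taken three days early matches an Arm A count on Day 1, at day 25. But the allowance is the same in both arms, so it widens both ranges without removing the offset. Section 7.2.4 words it for cycle 1 only, whereas Tables 9 and 10 also star later cycles.

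**The Day 1 wording can be reconciled.** Section 6.5.2.1 also says: "Patients should be monitored prior to each dose for platelet and neutrophil counts". A Day 1 count does precede Day 4 chemotherapy, so this need not contradict the Day 1 rule. The text still leaves open whether Arm A needs a further count on Day 4, and none is scheduled.

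**Conclusion.** The 3-day offset is exact, follows from the protocol's own schedule, and is not corrected anywhere. If counts are still recovering 25 to 28 days after carboplatin/PLD, the comparison of laboratory change at scheduled time points, and low-count adverse events that arise through treatment modification, will overstate the marrow toxicity attributable to APR-246. The size cannot be determined from the documents: nil at a plateau by day 25, from about one percentage point to well over ten per Day 1 count under the assumptions shown.

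Delays and dose reductions in Arm A are genuine consequences of that regimen, but should not be read as pure APR-246 marrow toxicity. The primary PFS analysis is not called into question. This is an inexpensive improvement to the safety analysis, not a flaw in the trial's main inference.

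**What to change.** **In Section 9.5.1:**
1. Keep the planned maximum-grade summary.
2. Add that ANC, platelets and hemoglobin will be summarized and compared between arms by actual days since the last carboplatin/PLD dose, either on matched days or with days since chemotherapy as a covariate.
3. Add a by-arm table of chemotherapy delays and reductions that shows the days since chemotherapy of the triggering count, with a note stating the 3-day offset.

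The cost is a little extra analysis, with no change to sample size or the primary analysis. The limitation is overlap: on schedule the arms meet only around day 25, so arm and days since chemotherapy are nearly confounded and the adjustment may be imprecise. Counts after a delay come from selected, slower-recovering patients and are a poor substitute.

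**Optional:** collect an Arm B count 25 days after chemotherapy in cycles 2-6, for analysis only, and state that it does not govern dosing. That statement is needed because a count inside the look-back window could otherwise stand in for the Day 1 dosing count. It may mean a second draw: at most 5 per patient, or 5 × 200 = 1,000 if Arm B reaches 200 patients.

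**For the sponsor to reconcile:** the Day 1 assessment in Sections 6.5.1.1 and 6.5.2.1 with the monitoring before each dose in Section 6.5.2.1, for Arm A; and the look-back wording in Section 7.2.4 with Tables 9 and 10. No dosing rule is proposed here.
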